7.1 Definitions

An Adverse Event (AE) is any undesirable clinical event occurring to a subject enrolled in the trial, whether or not it is considered related to the investigational product. This includes a change in a patient's clinical condition including changes in neurological status or laboratory results that has or could have a deleterious effect on the patient's health or well-being.

An Adverse Device Effect (ADE) is any AE related to the deployment of any coil type.

A Serious Adverse Event (SAE) or a Serious Adverse Device Effect (SADE) is an event that:

- Results in death
- Is life threatening
- Is disabling
- Requires initial or prolonged hospitalization (does not include planned hospitalization)
- Requires intervention to prevent permanent impairment / damage

An Unanticipated Adverse Device Effect (UADE) is any serious adverse effect on health or safety or any life threatening problem or death caused by, or associated with, a device, if that effect, problem or death was not previously identified in nature, severity or degree of incidence in the investigational plan, or any other unanticipated serious problem associated with a device that relates to the rights, safety, or welfare of subjects.

See Figure 3 for a classification of adverse events.

7.2 Reporting of Adverse Events

For this post-market study, only AE/SAEs that are related to the procedure, device or a change in neurological status should be captured on eCRFs and in the Subject's medical records, for both treatment arms. In case of occurrence of any SAE and/or UADE, the site's principal investigator shall promptly submit a report along with any other required documentation to the Sponsor, Northwestern University and funder, MicroVention, Inc and follow site-specific IRB procedures.

If there is a serious adverse event, the clinical study site will report such to the Sponsor, Northwestern University and the funder, MicroVention, Inc within 24 hours of learning the event.

If there is an unanticipated adverse device effect, the Principal Investigator will submit a report to the Sponsor, Northwestern University and the funder, MicroVention, Inc and to the reviewing IRB as soon as possible, but not later than 10 working days after the investigator learns of the effect.

All other reportable events should be reported no later than 10 working days after the investigator or site first become aware of the adverse event in question.

The adverse event report should at least include the following parameters:

- Date of event and time
- Type of event (E.g., AE, SAE, UADE)
- Narrative
- Duration of adverse event or adverse device effects (start-end)
- Treatment
- Outcome/Resolution Status

The principal investigator and the principal investigator of the site shall present any additional information or documentation (e.g. imaging results) to the DSMB and steering committee if required by these committees.

7.3 Expected Risks

Known risks associated with aneurysm coiling are as follows:

- Aseptic meningitis
- Inflammation
- Thromboembolic events
- Stroke
- Vasospasm
- Hydrocephalus
- Aneurysm Rupture
- Coil protrusion into parent vessel
- Parent Vessel Occlusion
- Premature coil detachment (coil breakage due to technical device malfunction)
- Death

8 Ethics and Regulatory Considerations

8.1 Subject Information and Consent Procedures

The Investigator, study coordinator or any other member of the research team approved by the IRB will obtain written informed consent from the patient or his/her LAR before subjecting her/him to study assessment procedures. The Subject will be clearly informed that the principal investigator, study coordinator and study monitor of the coordinating site (Northwestern University) will have access to personally identifiable information for the purposes of monitoring data against source documentation. However, only de-identified data is entered into the study database.

Each site participating in this study will have their own consent form that must be approved by their IRB. In addition, a study consent form approved by the primary site IRB will be provided to each clinical site. Only the local participating site consent form should be signed prior to enrollment and treatment. The coordinating site must receive and approve each participating site's ICF. Each Investigational site must provide to the Sponsor or Principal Investigator a copy of its IRB approved ICF, renewed approvals and signed patient consents, as appropriate, for the duration of the study.

The original, signed and dated ICF should be retained in the Subject's study records, and a copy provided to the Subject. Documentation of the informed consent process should also be retained in the subject's study records.

8.2 IRB Approval

The Investigator or the study coordinator is responsible for submitting the study protocol and any changes issued by the Sponsor during the course of the study for IRB approval prior to any Subject enrollment and amendments taking effect as well as obtain renewals at periods determined by the IRB for the duration of the study.

9 Statistical Methods

Primary analysis of primary and secondary outcomes will be based on the intent-to-treat (ITT) principle. Secondary analyses will examine differences based on per protocol principles, as well as a detailed analysis of missing data, should there be any (see below).

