“HEAT”

New Generation **H**ydrogel **E**ndovascular **A**neurysm treatment **T**rial

September 4, 2014
Protocol #1908: Version 07

A randomized controlled trial of new generation Hydrogel
coils versus bare platinum coils in the endovascular
treatment of intracranial aneurysms

Sponsor: **Northwestern University**
[name].
[name]
[name]
[contact]
[contact]

Funder: **MicroVention, Inc.**
[name]
[name]

This protocol contains confidential information for use by the Investigators and their designated representatives participating in this clinical investigation. It should be held confidential and maintained in a secure location. By accepting this document, you agree to maintain the information as confidential and to use it only for the purpose of conducting the study.

1 Protocol Synopsis

FULL STUDY TITLE	New Generation Hydrogel Endovascular Aneurysm Treatment Trial
STUDY OBJECTIVES	Comparing initial complete occlusion, recanalization, retreatment and adverse event rates of the HydroCoil® Embolic System to those of bare platinum coils.
STUDY DESIGN	International, randomized, prospective, controlled, multicenter trial
DEVICES	Second generation hydrogel coils from the HydroCoil® Embolic System™ (including the HydroSoft®, HydroFill® and HydroFrame® and future FDA and HPB approved Hydrogel coils) (“Hydrogel Group”) and Platinum coils (“Platinum Group”)
TREATMENT POPULATION	Subjects with intracranial aneurysms between the ages of 18 and 75 years inclusive
ESTIMATED TRIAL SIZE	600 randomized subjects
NUMBER OF SITES	Approximately 50 sites inside and outside of the U.S.
PRIMARY ENDPOINT	Aneurysm recurrence at any point during follow-up defined as any progression on the Raymond aneurysm occlusion scale.
SECONDARY ENDPOINTS	
• Packing density as measured by volumetric filling of the aneurysm• Clinical outcome at 18 to 24 months (mRS)• Peri-procedural and post-procedural adverse events related to the procedure and/or the device.• Mortality rate• Initial complete occlusion• Aneurysm retreatment• Hemorrhage from target aneurysm during follow-up• Aneurysm occlusion stability• Major vs. minor recurrence
VISIT SCHEDULE	Baseline, Procedure, 1 day post-procedure, 3 days to 28 days, 3 months to 12 months, 18 months to 24 months
PRINCIPAL INVESTIGATOR OF THE STUDY	[name]. [name] [name] [contact] [contact]

**CORE
LABORATORY
("CORE LAB")**

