5.2 Study Duration and Enrollment

The duration of the open enrollment phase will be 24 months or until the required number of patients are enrolled. Each patient will have a post-procedure follow-up of at least 18 months.

The number of Subjects to be enrolled, and randomized, in the study is up to 600. This sample size calculated to provide sufficient statistical power to show the anticipated difference in initial occlusion and recurrence rates between the 2 study arms (see section 9 for detailed statistical analysis). Patients will be recruited from up to 50 national and international centers. Each Investigational Site will be expected to enroll at least 20 Subjects. Each site must meet the eligibility criteria.

A multidisciplinary approach is expected from each qualified study center. The Neurovascular teams should include the appropriate specialties for the proper conduct of the study e.g., neurointerventionalist(s), experienced in intracranial aneurysm coiling, neurosurgeon(s), and study coordinator(s). In addition, the treating physician must meet a minimal level of expertise consisting of at least 5 successful intracranial aneurysm coiling procedures utilizing the HydroCoil Embolic system prior to enrolling patients into the study.

Each site must provide written approval from their reviewing Institutional Review Board (IRB) and all other required regulatory documentation prior to consenting and enrolling the first Subject.

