6.3 Randomization

Subjects who meet study inclusion and exclusion criteria and who have signed an informed consent form will be randomized through the study's Electronic Data Capture (EDC). Randomization will be performed through the EDC on the day of the coiling procedure. This must be completed once pre-coiling imaging has been reviewed and immediately before endovascular coiling begins. At this time, the Subject will be given a unique study identification number generated by the EDC. This number should be used on all study documents so that data is reported anonymously to protect subject confidentiality and patient health information (PHI). Patients will be randomized 1:1 to one of two study arms: 1) The HydroCoil® Embolic System ("Hydrogel Group") or 2) bare platinum coils ("Platinum Group").

Patient safety is a priority. In the event the treating investigator deems it clinically necessary to switch a subject randomized to the Hydrogel arm to the platinum coils arm for safety reasons, the crossover should be documented as a protocol deviation in the eCRF. However, the subject will continue to be followed and will receive all study-related procedures as per protocol. Similarly, if the investigator switches a subject, randomized to the bare platinum arm to the Hydrogel arm or uses more than 10% platinum coils (based on length) in a subject randomized to the Hydrogel arm, the same procedures will be followed. The reason(s) for the preference of one type of coils over the other will be documented in the eCRF.

If during the course of the treatment the investigator decides to perform staged coiling or to use a flow-diverting stent (e.g. pipeline), a protocol deviation should be documented in the eCRF and the subject should continue to be followed as per protocol.

If during the course of the treatment the investigator decides to switch to open surgery or decides not to treat the aneurysm at all, a protocol deviation should be documented and subjects should continue to be followed according to standard of care (i.e. as per site management protocol). The reason for the preference of surgery or no treatment over coiling will be documented on the eCRF.

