9.1 Sample Size Estimation

For univariate associations, using a two-sided two-sample test of proportions (Chi-square test), Table 5 shows the effect sizes one would be able to detect for given baseline rates (assuming 1:1 randomization and 5% type I error rate) at 80% power.

Using multiple logistic regression to predict recurrence (baseline rate in Platinum group of 33%), the sample of 600 patients would provide 80% power to detect an odds ratio between 0.60 and 0.47, depending on the r-squared of the other covariates to coils (between 0-0.2; note r-squared of 0 corresponds to hydrogel rate of 22.8% as in the univariate analysis). Likewise, for complete occlusion (baseline rate of .556), a sample of 600 provides 80% power to detect odds ratios between 1.60-1.70, depending on the r-squared of the other covariates to coils (between 0-0.2; note r-squared of 0 corresponds to hydrogel rate of .678 as above). Similarly, for recanalization, one would have 80% power to detect odds ratios between 0.613-0.577 (n=600).

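### Device-related adverse events are compared only by assigned arm or in an undefined per-protocol set; with coil switching provided for, no planned analysis compares them by device exposure

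*Combined protocol and SAP*

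**What the plan says.** The synopsis lists among the secondary endpoints "Peri-procedural and post-procedural adverse events related to the procedure and/or the device". Section 4.3 adds procedure- or device-related morbidity and mortality. Section 4.4 lists further safety outcomes, such as aseptic meningitis and thromboembolic events, and assigns them no analysis set.

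The opening of section 9 states: "Primary analysis of primary and secondary outcomes will be based on the intent-to-treat (ITT) principle". The next sentence plans secondary per-protocol analyses but does not say who belongs to that population. Section 9.2.2 analyses the remaining binary outcomes with the methods of the primary endpoint.

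Section 6.3 foresees a switch from hydrogel to platinum for safety reasons, recorded as a protocol deviation with follow-up continued. The same handling applies "if the investigator switches a subject, randomized to the bare platinum arm to the Hydrogel arm or uses more than 10% platinum coils". It also foresees that the operator turns to open surgery or leaves the aneurysm untreated. The reason is recorded in each case. Section 9 names no analysis by coil received.

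**The concern.** A device-related event is a question about the device that was used. Comparison by assigned arm answers a different question once coil types are switched, in two ways:

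- A subject assigned platinum but given hydrogel who has a hydrogel-related event counts against platinum.
- A subject assigned hydrogel who never received it, because of a switch beforehand, surgery or no treatment, adds to the hydrogel denominator without being exposed.

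Both tend to pull the arms together. For an efficacy claim of superiority that is the cautious direction. For harm it is not, because it makes a difference between devices harder to see. The per-protocol analysis cannot be relied on to fill the gap. Its population is undefined, and if it excludes switched subjects, as such sets often do, it drops their events instead of assigning them to a device.

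**Working it through.** **The plan's own figure.** Section 9.1 and Table 5 give 80% power for recurrence of 33.0% versus 22.8% with 600 subjects (two-sided chi-square test, 5%, 1:1). With 300 per arm and mean rate 27.9%:

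- Null SE = √(2 × 0.279 × 0.721 / 300) = 0.0366
- Alternative SE = √((0.33 × 0.67 + 0.228 × 0.772) / 300) = 0.0364
- z = (0.102 - 1.96 × 0.0366) / 0.0364 = 0.83, so power is 79.7%

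The figure reproduces. Table 5 has no adverse-event row, so what follows rests on assumed rates.

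**Dilution under ITT.** Let pH and pP be the event risks with each coil, cH the proportion switched from hydrogel to platinum, and cP the reverse. Assume that switching is unrelated to risk and that events follow the coil received.

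- Hydrogel arm: (1 - cH) × pH + cH × pP
- Platinum arm: (1 - cP) × pP + cP × pH
- ITT difference: (1 - cH - cP) × (pH - pP)

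With assumed risks of 6% and 2% (true difference 4.00 points):

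| cH | cP | ITT hydrogel | ITT platinum | ITT difference | Lost |
|---|---|---|---|---|---|
| 2% | 2% | 5.92% | 2.08% | 3.84 | 4% |
| 5% | 2% | 5.80% | 2.08% | 3.72 | 7% |
| 10% | 2% | 5.60% | 2.08% | 3.52 | 12% |
| 10% | 5% | 5.60% | 2.20% | 3.40 | 15% |

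With 300 per arm, power for 6% versus 2% is 70.6% without switching, 67.1% at 2% each way, and 57.6% at 10% and 5%.

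**What an as-exposed rule recovers.** Count a subject as hydrogel-exposed if any hydrogel coil was introduced, even if removed. Take 10% and 2%, that is 30 and 6 subjects of 300.

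- *Every hydrogel switch came before any hydrogel coil was introduced.* The groups then match the coil received, and the full 4.00 points return.
- *Every hydrogel switch followed a hydrogel attempt, with events still at the platinum risk.* Those 30 subjects stay in the hydrogel group, as under ITT. Events are 300 × 5.60% + 6 × 6% = 17.16 among 306, or 5.61%, against 2.00% for platinum only. The difference is 3.61, so 0.09 of the 0.48 points lost is recovered. At 10% and 5% it is 17.70/315 = 5.62%, a difference of 3.62 (0.22 of 0.60 recovered). At 5% and 2% it is 17.76/306 = 5.80%, a difference of 3.80 (0.08 of 0.28).
- *Every hydrogel switch followed an attempt that carried the full hydrogel risk.* ITT gives 6.00% - 2.08% = 3.92. Only the platinum-to-hydrogel part is lost, and the rule restores it.

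The rule thus recovers the part due to platinum-to-hydrogel switches and to hydrogel subjects in whom no hydrogel coil was introduced, and no more.

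**The case against.** A reader might infer that ITT generally charges an event to the wrong coil. The documents do not support that. Section 6.3 places randomisation immediately before coiling, so a hydrogel switch may well follow a hydrogel attempt. Where it follows a hydrogel problem, ITT counts that problem against hydrogel, which is correct.

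A reader might also infer that the per-protocol analysis removes subjects switched for safety. That is plausible, because section 6.3 classes the switch as a deviation, but section 9 does not say so.

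Third, a reader might take 7% to 15% as the loss to expect and as what an exposure table would restore. The rates behind those figures are assumed, and the restored part can be small. The loss is also modest against sampling error. For 6% versus 2% with 300 per arm the standard error is √(0.06 × 0.94 / 300 + 0.02 × 0.98 / 300) = 1.6 points, while the dilution in the 7% to 15% scenarios is 0.28 to 0.60 points.

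There are safeguards. Section 6.6.1 asks operators to use the randomised coil as far as possible, section 6.3 records reasons for switching, and section 12.1 sends serious events and device effects to the DSMB for assessment of relatedness. A device harm is therefore not invisible. But case review is not a between-device comparison. Section 9.2.1 speaks of comparing recurrence by coil type, but the ITT statement governs and the interaction models there use the randomisation group.

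These objections limit the size of the point and the benefit of the repair. The gap remains: no planned analysis compares device events by exposure.

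**Conclusion.** The point holds in a limited form. Device-related adverse events fall under ITT, the only alternative is an undefined per-protocol analysis, switching is provided for in both directions, and no exposure-based comparison is planned.

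The loss cannot be sized from the documents. It is 4% of the true difference at 2% switching each way and 12% at 10% and 2%, provided that switching is unrelated to risk and events follow the coil received. It is smaller where hydrogel switches follow a hydrogel problem. The formula covers switches between coil types. Subjects who end up with no coil add to the denominators, and how often that happens is not stated either. No conclusion of the trial is shown to change. The case for acting is that the remedy is cheap and that an exposure analysis added after the data are seen would be post hoc.

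**What to change.** Keep ITT for all outcomes. In section 9, for procedure- and device-related adverse events and the section 4.4 safety outcomes, add a supplementary as-exposed analysis shown beside ITT:

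- Include all treated subjects, and drop none for switching.
- Compare subjects with any hydrogel coil introduced, even if later removed, with subjects given platinum only.
- List every event in a switched subject with the reason for the switch, whether the event came before or after it, and the coil type involved. This shows cases that the rule would misplace, such as a platinum event before a switch to hydrogel.
- Define the per-protocol population, and report switches by arm and reason.

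The cost is about one paragraph and one extra set of safety tables. Reasons for switching are already captured. The documents do not confirm that coils introduced and then removed are recorded, and the minimum adverse-event report in section 7.2 has no item for coil type, so one or two eCRF fields may be needed. The downside is that operators choose the switch, so exposure groups are not purely randomised and may be confounded by aneurysm difficulty. The table therefore supplements ITT and does not replace it.

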9.1 Sample Size Estimation

For univariate associations, using a two-sided two-sample test of proportions (Chi-square test), Table 5 shows the effect sizes one would be able to detect for given baseline rates (assuming 1:1 randomization and 5% type I error rate) at 80% power.

Using multiple logistic regression to predict recurrence (baseline rate in Platinum group of 33%), the sample of 600 patients would provide 80% power to detect an odds ratio between 0.60 and 0.47, depending on the r-squared of the other covariates to coils (between 0-0.2; note r-squared of 0 corresponds to hydrogel rate of 22.8% as in the univariate analysis). Likewise, for complete occlusion (baseline rate of .556), a sample of 600 provides 80% power to detect odds ratios between 1.60-1.70, depending on the r-squared of the other covariates to coils (between 0-0.2; note r-squared of 0 corresponds to hydrogel rate of .678 as above). Similarly, for recanalization, one would have 80% power to detect odds ratios between 0.613-0.577 (n=600).

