6.1 Screening and Consent

Eligibility will be assessed once the neurovascular team makes a decision on endovascular treatment of an aneurysm. A local site log of all eligible patients will be kept and a copy returned to the coordinating site (Northwestern University) when requested by the study monitor.

If a patient fulfills the inclusion and exclusion criteria, an authorized member of the research team will discuss the trial and provide the patient or his/her LAR with the informed consent form. The patient or LAR will be provided adequate time to consider participation in the trial and the research team will answer all questions regarding the trial. A copy of the consent will be retained in the patient's medical record, one will be given to the patient, and the original will be retained by the local site.

All patients who meet the eligibility criteria and give written informed consent are eligible for enrollment into the study which occurs at the time of randomization

Screen failures are defined as a subject consented and screened for enrollment, but not ultimately enrolled on the day of randomization; provided that the failure to enroll was attributable to the subject's failure to meet the inclusion or exclusion criteria listed in the protocol.

Screen failures and subjects who electively withdraw from the study will be dropped from any further follow-up and statistical analysis of this study. The original ICF and any data collected up until the date of withdrawal will be maintained in the clinical site's study files and their number will not be used again in the study.

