6.9 Early follow-up Visit: Between 3 months to 12 months post-coiling

Clinical and neurological assessments will be performed. The neurological examination will include the mRS. The investigator or an authorized member of the research team will assess for any new or unresolved adverse events. A digital subtraction cerebral angiogram will be performed. MRA can be performed instead of or in addition to the angiogram if considered standard of care at the institution. Quality of life will be assessed with the SF-36 questionnaire. For subjects enrolled with ruptured aneurysms, an NIHSS score will also be obtained.

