9.2 Statistical Analysis Plan

9.2.1 Primary endpoints:

Chi-square tests (simple logistic regression) will be used to determine if rates of recurrence differ by coil type. Additionally, multiple logistic regression models will be used to examine those rates while adjusting for various covariates, including, but not limited to: site, age, gender, aneurysm size, neck size, packing density and rupture status. Models will be fit to examine potential interactions between covariates and randomization group in predicting outcomes; and final models will be fit depending on statistical and clinical significance of the covariates to the outcome as well as any change in the relationship between the randomization group and outcome. Analyses will be presented both as univariate and adjusted Odds Ratios and corresponding [Wald] 95% Confidence intervals.

While the study has been designed to minimize any missing data due to this being a longitudinal study, the potential for missing data or loss to follow-up is present. Patterns of missing data and dropout will be examined to determine if complete case analysis or available data analyses are appropriate or if imputation methods will need to be incorporated. Should a complete case analysis be appropriate, PROC LOGISTIC will be used to analyze these binary outcomes; otherwise PROC GLIMMIX will be used for an available data analysis. If imputation methods are called for, PROC MI and PROC MIANALYSE will be used and results presented. All analyses will be run at a type I error rate of 5% using SASv9.2, Cary, NC.

9.2.2 Secondary endpoints:

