¹ For Subjects enrolled with ruptured aneurysms² According to standard of care of each institution.³ For Subjects with ruptured aneurysms who are unable to complete the SF-36 prior to procedure, the SF-36 can be completed prior to subject discharge following procedure.

Table 5. Effect Sizes for outcomes with N=600, with 80% power

Outcome	baseline (platinum) rates	Hydrocoil rates	% change
Recurrence	33.0%	22.8%	-30.9%
Complete occlusion	55.6%	66.7%	20%
	47.6%	59.0%	23.9%
Complete or nearly complete occlusion	85.5%	92.6%	8.4%
Retreatment	17.4%	9.6%	-44.8%

Table 6. Electronic Data Entry Timelines

eCRF	Timeline
Adverse Event eCRF	
In the event of a serious adverse event, complete the AE CRF on the web-based database and fax report within 24 hours of learning of the event to the Sponsor and Funder. Comply with local reviewing IRB reporting rules.
 
In the event of an unanticipated adverse device effect, complete the AE CRF on the web-based database and fax report as soon as possible, but no later than 10 working days after the investigator first learns of the effect to the Sponsor and Funder. Comply with local reviewing IRB reporting rules.

All other eCRFs	Within 5 business days of subject discharge or follow-up

Table 7: Required Imaging Schedule

HydroCoil Embolic System Clinical Trial	Screening & Baseline	Surgery		Post-Procedure Follow-up	Immediate Follow-up	Early Follow-up	Final Follow-up
		Pre-Coil	Post-Coil				
Schedule of Events	Up to 30 days prior to surgery			Day 1	3-28 Days	3-12 Months	18-24 Months
Angiogram		X	X			X	X
MRA						X ²	X ²

² According to standard of care at each institution

Please note that if an angiogram, MRA or CTA is performed 30 days before surgery, the Imaging eCRF should be completed and the CD shipped to the core lab and Northwestern University. This imaging is optional and is not required for the study.

Results of MRIs or CTs are not needed

Figure 1. Aneurysm occlusion grading system as reported by Meyers et al.²³

[figure not shown]

Figure 2. Raymond angiographic classification of residual coiled aneurysm.

[figure not shown]

Figure 3: Classification of Adverse Events

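### The 80% power for recurrence assumes all 600 randomised patients have follow-up imaging, with no allowance for loss; two printed figures in 9.1 (0.47 and .678) also need correcting

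*Combined protocol and SAP*

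**What the plan says.** Section 9.1 bases its calculations on a two-sided chi-square test, 1:1 allocation, 5% type I error and 80% power. Table 5 is headed "Effect Sizes for outcomes with N=600, with 80% power" and gives recurrence of 33.0% on platinum against 22.8% on hydrogel. For the adjusted analysis, 9.1 says "the sample of 600 patients would provide 80% power to detect an odds ratio between 0.60 and 0.47" as the R-squared of the other covariates with coil type runs from 0 to 0.2. For complete occlusion (baseline .556) it gives odds ratios of 1.60 to 1.70 over the same range, with the remark "note r-squared of 0 corresponds to hydrogel rate of .678 as above". Table 5 prints 66.7% for that rate. For recanalization, 9.1 gives 0.613 to 0.577 without a baseline.

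On numbers, section 5.2 says "The number of Subjects to be enrolled, and randomized, in the study is up to 600"; the synopsis also gives 600 as the number randomised. On losses:

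- Section 6.1: "subjects who electively withdraw from the study will be dropped from any further follow-up and statistical analysis of this study". Section 5.3.1 differs, allowing use of data obtained before withdrawal.
- Section 6.3 moves patients switched to open surgery, or left untreated, to the site's own follow-up.
- Section 6.13 lists withdrawal, loss to follow-up and death as exits.
- Section 9.2.1 accepts that "the potential for missing data or loss to follow-up is present".

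No section states an expected loss or inflates the sample size.

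**The concern.** Recurrence is progression on the Raymond scale at any time in follow-up (section 4.2), so a patient contributes to the primary comparison only with at least one usable follow-up angiogram or MRA. If 600 is both the most that can be randomised and the number assumed analysed, the stated power is reached only with no loss at all. Any loss makes it too high, and a null primary result would then be read as coming from a better-powered trial than was run.

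The two misprints are a separate matter. They make the trial look less sensitive than it is, but they put 9.1 at odds with Table 5 and with its own odds ratios.

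**Working it through.** **Inputs.** Two-sided alpha 0.05, 1:1, 80% power, N = 600 (9.1 and Table 5); platinum recurrence p1 = 0.33, hydrogel p2 = 0.228; complete-occlusion baseline 0.556; R-squared 0 to 0.2. The loss rates below are assumptions, because the documents give none.

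**Formula.** With n per arm and p̄ = (p1 + p2)/2,

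power = Φ{ [ |p1 − p2| − 1.96 √(2p̄(1 − p̄)/n) ] / √([p1(1 − p1) + p2(1 − p2)]/n) }.

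For the adjusted analysis, n is multiplied by (1 − R²).

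**1. The plan's own figures at 600 evaluable.** For recurrence, n = 300, the difference is 0.102, the null standard error is 0.03662 and the alternative standard error is 0.03638. Power = Φ[(0.102 − 1.96 × 0.03662)/0.03638] = Φ(0.831) = 79.7%. The five rows of Table 5, in order, give 79.7%, 79.8%, 80.1%, 79.7% and 80.0%. Table 5 is therefore right if all 600 are analysed, and it has no slack.

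**2. Recurrence with fewer evaluable patients.**

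| Assumed loss | Evaluable | Power, 33% vs 22.8% | Hydrogel rate detectable at 80% power |
|---|---|---|---|
| 0% | 600 | 79.7% | 22.8% (OR 0.60) |
| 5% | 570 | 77.6% | 22.5% (OR 0.59) |
| 10% | 540 | 75.4% | 22.2% (OR 0.58) |
| 15% | 510 | 73.0% | 22.0% (OR 0.57) |
| 20% | 480 | 70.4% | 21.6% (OR 0.56) |

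Simulating the chi-square test (400,000 trials per row) gives 79.8%, 77.8%, 75.7%, 73.1% and 70.6%. For context, follow-up in the studies listed in Table 2 ran from 51% to 90%. At those two extremes (306 and 540 evaluable) power would be about 51% and 75%.

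**3. The 0.47.** At R² = 0.2 the effective n is 300 × 0.8 = 240 per arm. Solving for 80% power gives p2 = 0.2163, so OR = (0.2163/0.7837)/(0.33/0.67) = 0.560. The same method returns 0.598 at R² = 0, matching the printed 0.60, and 1.601 and 1.697 for occlusion, matching the printed 1.60 to 1.70. An OR of 0.47 means p2 = 0.188, which needs 149 per arm for 80% power. That implies R² = 1 − 149/300, about 0.50. At R² = 0.2 an OR of 0.47 has 94.7% power. Continuity correction (0.548), unpooled variance (0.562), a Wald test on the log odds ratio (0.558), one-sided alpha (0.601) and 90% power (0.508) do not give 0.47 either. A hidden loss allowance does not explain it: at R² = 0.2 it would correspond to 298/0.8, about 370 evaluable. With losses of 10% and 20% the adjusted detectable OR at R² = 0.2 is 0.54 and 0.52.

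**4. The .678.** An OR of 1.60 from 0.556 gives 0.667, as in Table 5. A rate of 0.678 gives OR = (0.678/0.322)/(0.556/0.444) = 1.68 and 86.9% power at 600, so it is not the rate at R² = 0.

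**5. Recanalization.** Working backwards, 0.613 to 0.577 fits N = 600 with a baseline of about 38%: 0.6125 and 0.5761 at 38%. The range is coherent, but neither 9.1 nor Table 5 states the baseline.

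**The case against.** The strongest reply is that little is lost in practice. Table 5 reports detectable effects, and on that scale a 10% loss moves the hydrogel rate by 0.6 percentage points and a 20% loss by 1.2. The endpoint counts recurrence at any time, there are two scheduled imaging visits, and "MRA can be performed instead of or in addition to the angiogram if considered standard of care at the institution", so a patient who misses one image may still be evaluable. Inclusion criterion 6 and exclusion criteria 12 and 14 select for patients who will return. Table 2 mixes retrospective and registry series and is a weak guide to loss here. Patients moved to site follow-up may still be imaged. Section 9 sets intention-to-treat as primary, and 9.2.1 plans a review of dropout patterns followed by complete-case, available-data or imputation analysis.

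Most of this stands as a limit on size. The relevant loss is only of patients with no usable follow-up image, its rate is unknown, and the modest shift in detectable rate is a fair way to express it. It does not remove the point: the plan makes no allowance for that group, and its analysis methods do not in general restore lost power. The initial-occlusion rows of Table 5 are unaffected. Nothing in the reply rescues 0.47 or .678, though both err on the cautious side and alone would be editorial. On recanalization, only the baseline label is missing.

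**Conclusion.** The concern holds. The base calculation is correct for 600 evaluable patients; the fault is that 600 is also the randomisation ceiling and no loss is allowed for. Power for 33% versus 22.8% is then below 80% by an amount that depends on an assumed loss: about 75% at 10% and 70% at 20%, on the unadjusted chi-square test with equal loss in the two arms. The direction is certain and the size is not. Separately, 0.47 should read 0.56 and .678 should read .667; neither slip overstates power. The design stands, but its power statement should be amended.

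**What to change.** In section 9.1 and Table 5, without changing enrolment:

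1. Label Table 5 as N = 600 evaluable.
2. State an assumed evaluable number for recurrence, with its power and detectable effect. As illustrations, 540 gives 75% power for 33% versus 22.8% and 80% power for 33% versus 22.2%; 480 gives 70% power, and 80% power for 33% versus 21.6% (OR 0.56). The sponsor should choose the number and say why.
3. Replace 0.47 with 0.56 and .678 with .667.
4. State the baseline behind the recanalization range 0.613 to 0.577 (minor).

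The cost is wording only. The recurrence power statement becomes less favourable, and the corrected adjusted odds ratio becomes more favourable.
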